1.1 Background

Multiple Sclerosis (MS) is a chronic, immune-mediated disease of the central nervous system characterized by inflammation, demyelination and axonal/neuronal destruction, ultimately leading to severe disability ([Trapp et al 1998](#), [Sospedra and Martin 2005](#)). Globally, the median estimated incidence of MS is 2.5 per 100,000 (ranging from 1.1 to 4.0 per 100,000) and the median estimated prevalence is 30.0 per 100,000 (ranging from 5.0 to 80.0 per 100,000) [WHO and Multiple Sclerosis International Federation. 2008](#). At diagnosis, approximately 85% of patients have relapsing-remitting MS (RRMS), characterized by recurrent, acute episodes (relapses) of neurological symptoms. Approximately 50% of these patients progress to secondary progressive MS (SPMS) within 10 years, 90% within 25 years, when a less inflammatory, and more neurodegenerative. SPMS can also be segregated based on whether patients continue to experience relapses (relapsing form of SPMS) or not (purely progressive SPMS). About 10-15% of MS patients present with a primary progressive course (PPMS) defined by a continuous accumulation of neurological disability from symptom onset without superimposed exacerbations or remissions. Progressive relapsing MS (PRMS; chronic progressive from onset with infrequent relapses) is the least frequent form of MS ([Keegan and Noseworthy 2002](#)). So typically recurrent acute episodes (relapses) of neurological symptoms, which are followed by a complete or partial recovery is the basic feature of MS.

In China, several therapies are approved for patients with RRMS and fall within 4 classes of products: anti-CD20 monoclonal antibody (ofatumumab), dimethyl fumarate, DHODH inhibitor (teriflunomide), and S1P receptor modulator (siponimod, fingolimod and ozanimod). All are considered as immunomodulatory or immunosuppressive medications. Beta interferons have multiple immune actions but the means by which the drugs are effective in MS remains unknown. They have shown modest (~30%) effect on relapses and in the case of IFN β -1a, on disability ([Goodin et al 2002](#)). Teriflunomide, an orally active drug that inhibits lymphocyte proliferation. It selectively and reversibly inhibits dihydro-orotate dehydrogenase, an enzyme in the de novo synthesis pathway of pyrimidines, resulting in reduced proliferation of peripheral T- and B- lymphocytes, and hence reduce numbers of lymphocytes crossing the blood-brain barrier and causing CNS damage ([Bar Or et al 2014](#)). Fingolimod (Gilenya) is a chemical entity for once daily oral administration which has been submitted to health authorities in the USA and in Europe late 2009 and subsequently in other countries worldwide to obtain market authorization. Since August 2010, fingolimod has been approved more than 70 countries for treatment of patients with relapsing of MS. Fingolimod is rapidly phosphorylated in vivo, and fingolimod-phosphate (fingolimod-P) acts as an agonist of G protein-coupled receptors for sphingosine-1 phosphate (S1P). More particularly, fingolimod-P acts as “super agonist” of the S1P₁ receptor on thymocytes and lymphocytes, inducing internalization and degradation of that receptor. This renders these cells unresponsive to S1P₁ signaling, thus depriving them of a signal necessary for egress from lymph nodes and secondary lymphoid tissues. The downstream result of this fingolimod induced interdiction of S1P₁ signaling is a marked reduction in the number of both B and T lymphocytes in the intravascular compartment and a decrease in recirculation of these cells to extravascular compartments, including the CNS.

Prior to submission, the efficacy profile of fingolimod was evaluated in five main studies. In two of the phase III clinical trials, Study CFTY720D2301 (acronym FREEDOMS I) and CFTY720D2309 (acronym FREEDOMS II), each 24-month placebo-controlled study, fingolimod demonstrated reduction of relapse rate, disability progression, MRI lesion counts and rate of brain atrophy (Kappos et al 2010). In another Phase III trial, study CFTY720D2302 (acronym TRANSFORMS), a large active controlled study vs. intramuscular interferon beta-1a, fingolimod showed a significant reduction in relapse rate over the 12-month treatment period and reduced magnetic resonance imaging (MRI) lesion counts and rate of brain atrophy Kappos et al 2010. Study CFTY720D2399 (acronym LONGTERMS), an open-label, phase IIIb extension study, indicated that fingolimod treatment for up to 14 years had a sustained benefits for control of disease activity and disability progression without emerging safety concerns Cohen et al 2019. In the controlled pediatric study CFTY720D2311 (acronym PARADIGMS), it compared the efficacy of fingolimod to intramuscular interferon beta-1a in pediatric patients. It showed the annualized relapse rate (ARR), was significantly lower in patients treated with fingolimod than in patients who received interferon beta-1a.

The safety profile of fingolimod has been well characterized with approximately 296,714 patients in both clinical trials and the post –marketing setting, with the total patient exposure now at approximately 746,745 patient year by 30 Nov 2019. The safety profile in pediatric patients was overall similar to that seen in adult patients Chitnis et al 2018.

During the course of the fingolimod clinical development, several areas were identified as safety areas of note: bradyarrhythmias upon treatment initiation or on restarting after an interruption of fingolimod therapy of more than 14 days, liver transaminase elevations, hypertension, macular edema and infection.

Initiation of fingolimod treatment results in a transient decrease in heart rate and infrequently induces atrio-ventricular (AV) block. In MS clinical trials, the mean maximal decrease in heart rate after the first dose intake was 12~ 13 bpm and was seen at ~6 hours post-dose. Heart rates below 40 beats per minute were rarely observed in patients on fingolimod 0.5 mg/day. Heart rate progressively returned to baseline within 1 month of dose initiation despite continued dosing. In addition, a mild increase in blood pressure of approximately 2 mmHg diastolic and 3 mmHg systolic on average. This onset after approximately 1 months of treatment initiation persisted with continued treatment but reversed upon cessation of therapy. Hypertension was reported as an adverse event in 6.5% of patients on fingolimod 0.5 mg/day and in 3.3 % of patients on placebo in the 2-years placebo controlled study.

Liver enzyme elevations were seen in clinical trials. Asymptomatic elevations in serum levels of hepatic transaminases ≥ 3 x upper limit of normal (ULN) and ≥ 5 x ULN, were observed in 8.0% and 1.8% of patients treated with fingolimod 0.5 mg/day respectively compared to 1.9% and 0.9% for patients receiving placebo. The majority of elevations occurred within 12 months of therapy and returned to normal, generally within 2 months of discontinuation of therapy.

Macular edema occurred in 0.5% of patients treated with fingolimod 0.5 mg/day. Approximately 75% of cases occurred within the first 3-4 months of therapy. The macular edema generally improved or resolved spontaneously after drug discontinuation. The risk of developing macular edema appears to be increased in MS patients with a history of uveitis. There is limited data on fingolimod in MS patients with diabetes mellitus. In earlier renal

transplant clinical studies where patients with diabetes mellitus were included, therapy with fingolimod 2.5 mg/day and 5 mg/day resulted in a 2-fold increase in the incidence of macular edema. MS patients with diabetes mellitus are therefore expected to be at a higher risk for macular edema.

A key pharmacodynamic effect of fingolimod is a dose-dependent reduction of peripheral lymphocyte count to 20 - 30% of baseline values. This is due to the reversible sequestration of lymphocytes in lymphoid tissues. In multiple sclerosis clinical trials, the overall rate of infections (65.1%) at the 0.5 mg dose was similar to placebo [Novartis 2019](#). However, bronchitis, herpes zoster and pneumonia, were more common in Gilenya treated patients [Karlsson G,Francis and Schmouder R,et 2009](#). Serious infections occurred at a rate of 1.6% in the fingolimod 0.5 mg group versus 1.4% in the placebo group [\(2013\) 2.5 Clinical Overview Rationale for changes to Core Data Sheet \(CDS\) / A full review and up date of sections, A full review and update of sections, “Warnings and Precautions”, “Adverse Drug Reactions” and “Interactions”](#) . In a second 2-year placebo controlled study, CFTYD2309, which was reported after approval of fingolimod, the safety profile seen in prior studies was largely confirmed, however in this study herpes zoster was reported more frequently in the fingolimod arms as compared to placebo (2.5% vs. 0.8% respectively) and basal cell carcinomas were more frequent in the fingolimod 0.5 mg group (2.8%) as compared to both, the fingolimod 1.25 mg and the placebo arms (1.6 and 0.6%) respectively. One fatal primary disseminated varicella zoster infection and one fatal herpes simplex encephalitis case have occurred in patients receiving the 1.25 mg/day dose; at the fingolimod 0.5 mg dose, one patient died in the post-marketing setting due to a disseminated varicella zoster infection in the context of high dose steroid treatment.

As part of a post-approval commitment to China's health authorities, Novartis is conducting this post-approval commitment study (PAC) in order to evaluate the efficacy and safety profile of fingolimod in Chinese multiple sclerosis patients. The study will collect safety profile information related to clinical practice setting and long-term follow-up including, but not limited to infections, cardiac and vascular events (e.g. stroke, myocardial infarction, angina pectoris and peripheral vascular disease, second and third degree AV conduction block, hypertension), malignancies, pulmonary events, seizures, MS relapses, atypical severe neurological events and sudden/unexplained death.

1.2 Purpose

The purpose of this study is to collect 24-month efficacy, safety, tolerability, and health outcome data of fingolimod (0.5 mg per Day) in participants with relapsing multiple sclerosis (RMS) in China. This is a post approval commitment study for fingolimod.

2 Objectives and endpoints

Table 2-1 Objectives and related endpoints

Objective(s)	Endpoint(s)
Primary objective(s)	Endpoint(s) for primary objective(s)

To evaluate the efficacy of fingolimod 0.5mg on annualized relapse rate (ARR) in	
Annualized relapse rate(ARR)

Objective(s)	Endpoint(s)
participants with RMS treated for up to 24 months.	
Secondary objective(s)	Endpoint(s) for secondary objective(s)

To evaluate the safety and tolerability of fingolimod 0.5 mg in participants with RMS treated for up to 24 months.To evaluate the efficacy of fingolimod 0.5 mg on MRI lesions.	
Adverse events (AE) and serious adverse events (SAE)Laboratory tests(hematology, biochemistry)Vital signsElectrocardiogram (ECG)Ophthalmology 
T1 hypo-intense lesion number and volume; T2 lesion volume, new/newly enlarged T2 lesion number; Gd-enhancing T1 lesion number and volume.

3 Study design

This is a 24-month, open-label, multicenter, interventional, single-arm study to collect efficacy, safety and health outcome data of fingolimod (Gilenya) 0.5 mg/day in approximately 100 relapsing multiple sclerosis (RMS) participants in China.

The study will consist of three Phases (see [Figure 3-1](#)):

Screening (up to 1 month): After signing informed consent, participants will enter a Screening Phase to determine eligibility according to inclusion and exclusion criteria.

[figure not shown]
The investigator must ensure that all patients meet the inclusion and exclusion criteria to be eligible to enter the study.

Treatment Period (24 months): On visit Day 1, all eligibility criteria will be confirmed, including a pre-dose ECG and vital signs. The first dose of study drug will be taken in the clinic on Day 1 and the participant will be monitored for at least 6 hours after the first dose administration before discharge. Refer to [Section 16.5](#) for Guidance for monitoring of patients taking their first dose of the study drug.

Then the participants should come to site and be evaluated month 1 and then every three months till the end of treatment up to 24 months.

Follow Up (2 months): Participants who completed Treatment Period will return for the Follow-up visit 2 months after the last dose of study drug.

Figure 3-1 Study design

4 Rationale

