1.2 Study objectives and endpoints

Table 1-1 Objectives and related endpoints

Objective(s)	Endpoint(s)
Primary objective(s)	Endpoint(s) for primary objective(s)

To evaluate the efficacy of fingolimod 0.5mg on annualized relapse rate (ARR) in subjects with RMS treated for up to 24 months.	
Annualized relapse rate (ARR)
Secondary objective(s)	Endpoint(s) for secondary objective(s)

To evaluate the safety and tolerability of fingolimod 0.5 mg in subjects with RMS treated for up to 24 months.	
Adverse events (AE) and serious adverse events (SAE)Laboratory tests (hematology, biochemistry)Vital signsElectrocardiogram (ECG)Ophthalmology

To evaluate the efficacy of fingolimod 0.5 mg on MRI lesions.	
T1 hypo-intense lesion number and volume; T2 lesion volume, new/newly enlarged T2 lesion number; Gd-enhancing T1 lesion number and volume.

2 Statistical methods

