2.7.1 Secondary endpoints

Secondary efficacy endpoints include:

- To estimate annualized rate of new or newly enlarged T2 lesions, below variables will be derived:
 - The total number of new or newly enlarged T2 lesions within 30 days from the last dose date will be derived by taking the sum of number of new or newly enlarged T2 lesions from all scheduled MRI scans (as compared to the previous scan) with a non-missing value within 30 days from the last dose date.
 - The time (in years) from screening scan will be calculated as (date of last scheduled MRI scan with a non-missing value for the number of new or enlarging T2 lesions within 30 days from the last dose date – date of screening scan +1)/365.25.
- Volume of T2 lesions.
- To estimate the number of Gd-enhancing T1 lesions per scan, below variables will be derived:
 - The total number of Gd-enhancing T1 lesions within 30 days from the last dose date will be derived by taking the sum of number of Gd-enhancing T1 lesions from the all scheduled MRI scan with a non-missing value within 30 days from the last dose date. Any Gd-enhanced T1 data obtained less than 30 days after the termination of steroid therapy which is used to treat MS relapses will not be included in analysis of Gd-enhancing T1 lesion related endpoint.
 - The number of MRI scans will be derived by counting the number of scheduled MRI scans with non-missing values for the number of Gd-enhancing T1 lesions within 30 days from the last dose date (i.e. the number of scans contributed to the derivation of the above variable: the total number of Gd-enhancing T1 lesions within 30 days from the last dose date).
- Volume of Gd-enhancing T1 lesions.
- Number of T1 hypo-intense lesions.
- Volume of T1 hypo-intense lesions.

Change and % change in volume of T2 lesions, Gd-enhancing T1 lesions and T1 hypo-intense lesions from baseline will only be defined for subjects with both baseline and post-baseline values and will be calculated as:

change from baseline = post-baseline value – baseline value;

% change from baseline = change from baseline / baseline value*100.

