2.7.2 Statistical hypothesis, model, and method of analysis

Methods of analyses for efficacy endpoints defined in [Section 2.7.1](#) are described below.

- The annualized rate of new or newly enlarged T2 lesions for Adult group will be estimated by a negative binomial regression model with log-link function, the total number of new or newly enlarged T2 lesions within 30 days from the last dose date (per subject) as the response variable. Natural log of time from screening scan in years will be used as the offset. The model will include baseline age and baseline volume of T2 lesions as continuous covariates. The estimated number of new or newly enlarged T2 lesions will be obtained together with the corresponding 95% confidence interval.

Supportive analyses: similar analyses may also be conducted to obtain the estimated annualized rate of new or newly enlarged T2 lesions at month 0 to month 12 and at month 12 to month 24 for Adult group.

Descriptive summary statistics (mean, median, standard deviation, min, max) for the number of new or newly enlarged T2 lesions will be provided by age group and by visit. Number and percentage of subjects free of new or newly enlarged T2 lesions will also be provided by age group.

- The number of Gd-enhancing T1 lesions per scan for Adult group will be estimated by a negative binomial regression model with log-link function, the total number of Gd-enhancing T1 lesions within 30 days from the last dose date (per subject) as the response variable. Natural log of the number of MRI scans will be used as the offset. The model will include baseline age and number of Gd-enhancing T1 lesions at baseline as continuous covariates. The estimated number of Gd-enhancing T1 lesions per scan will be obtained together with the corresponding 95% confidence interval.

Supportive analyses: descriptive summary statistics (mean, median, standard deviation, min, max) for the number of Gd-enhancing T1 lesions will be provided by age group and by visit. Number and percentage of subjects free of Gd-enhancing T1 lesions will also be provided by age group.

- Descriptive summary statistics (mean, median, standard deviation, min, max) will be provided by age group and by visit for the following: volume of T2 lesions, volume of Gd-enhancing T1 lesions, number of T1 hypo-intense lesions, volume of T1 hypo-intense lesions, change and % change in volume of T2 lesions, Gd-enhancing T1 lesions and T1 hypo-intense lesions from baseline.

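### T1 hypo-intense lesion number is a named secondary endpoint, but the SAP reports it only as raw counts by visit, with no within-participant change from baseline

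*Protocol*

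**What the plan says.** The MRI objective in Protocol Section 2, Table 2-1, is "To evaluate the efficacy of fingolimod 0.5 mg on MRI lesions". Its endpoints, repeated in SAP Table 1-1, include "T1 hypo-intense lesion number and volume; T2 lesion volume, new/newly enlarged T2 lesion number".

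Protocol 12.5 plans an analysis of T1 hypo-intense volume (change and percentage change) but none of the number. SAP 2.7.1 lists "Number of T1 hypo-intense lesions" with no further derivation. It then states "Change and % change in volume of T2 lesions, Gd-enhancing T1 lesions and T1 hypo-intense lesions from baseline will only be defined for subjects"; the definition requires a value at both time points. In that sentence the word volume governs the whole list, so the count is not covered.

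SAP 2.7.2 gives mean, median, SD, minimum and maximum, by age group and visit, for a list that includes "number of T1 hypo-intense lesions, volume of T1 hypo-intense lesions, change and % change in volume of T2 lesions". Again the change terms attach to volumes.

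The other two MRI counts are treated differently. New or newly enlarged T2 lesions are counted against the previous scan (SAP 2.7.1). For the Gd-enhancing T1 count, SAP 2.7.2 says "The model will include baseline age and number of Gd-enhancing T1 lesions at baseline as continuous covariates".

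SAP 2.7 and 2.7.3 restrict MRI analyses to scans within 30 days of last dose and do not impute missing values.

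**The concern.** The T1 hypo-intense count is a standing total. Participants enter with recent documented relapses (Protocol 5.1), so part of the total at any visit will predate the first dose. With no control arm, what the trial itself can show about this count on treatment is how it moves within participants, and that is not planned.

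Comparing raw means across visits is a weak substitute for two reasons:

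- It carries between-participant variation in lesion load that pairing would remove.
- The people contributing at Month 24 need not be those contributing at baseline. If participants with many lesions are more often absent, the raw mean can fall while those who remain gain lesions.

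What is at stake is the reading of one descriptive secondary endpoint, not the primary analysis.

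**Working it through.** **Plan figures.** Neither document gives a mean, SD, precision or missing-data rate for this count. The nearest planning figures are those for the relapse rate (Protocol 12.8.1, SAP 3.1), and they reproduce: 0.25 ± 1.96 × √((0.25 + 0.25²)/80) = 0.1275 to 0.3725, stated as 0.13 to 0.37; and 80/(1 − 0.20) = 100. Only the 100 participants and the 20% are borrowed below.

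**Assumed inputs, not from the documents.**
- Baseline count negative binomial with mean m = 5, 10 or 20 and k = 1. (The SAP's k = 1 is for relapses, not lesions.)
- True gain over 24 months negative binomial with mean 0.7 and k = 1, unrelated to baseline count or absence.
- All 20% absent at Month 24.

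**Precision, absence unrelated to baseline.** Baseline variance is σ² = m + m² = 30, 110, 420. Gain variance is 0.7 + 0.7² = 1.19.

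- Paired change in 80 participants: SE = √(1.19/80) = 0.122.
- Raw Month 24 mean (80) minus raw baseline mean (100), where the 80 belong to the 100: SE = √(σ² × (1/80 − 1/100) + 1.19/80).

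| Baseline mean | SE, raw difference | SE, paired | Ratio |
|---|---|---|---|
| 5 | √(0.075 + 0.0149) = 0.30 | 0.122 | 2.5 |
| 10 | √(0.275 + 0.0149) = 0.54 | 0.122 | 4.4 |
| 20 | √(1.05 + 0.0149) = 1.03 | 0.122 | 8.5 |

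Simulation agrees, with ratios of about 2.5 to 9.

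**Sign of the raw difference (simulation).** The true change is +0.7 throughout, and the paired mean change stays at +0.7 in every row. Dependence is the log-odds of absence per log unit of baseline count (plus one).

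| Absent at Month 24 | Dependence on baseline | Raw difference negative, means 5 / 10 / 20 |
|---|---|---|
| 20% | none | 2% / 10% / 23% |
| 20% | 0.25 | 7% / 33% / 57% |
| 20% | 0.5 | 22% / 60% / 83% |
| 10% | 0.5 | 4% / 28% / 57% |

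With 20% absent and dependence 0.5, the raw difference averages about +0.25, −0.2 and −1.15 at the three baseline means.

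**Sensitivity to how closely repeat scans agree.** The model above has no reading error, so baseline and Month 24 counts are almost perfectly correlated (√(30/31.19) = 0.98 at mean 5). With equal SDs s and correlation ρ, the variance of the raw difference is s² × (1/80 + 1/100 − 2ρ/100), and that of the paired change is s² × 2(1 − ρ)/80. The SE ratio is √((0.0225 − 0.02ρ)/(0.025 − 0.025ρ)), which is 1.1, 1.1, 1.3 and 1.7 at ρ = 0.7, 0.8, 0.9 and 0.95. The precision gain therefore shrinks if repeat counts agree less well. The selection shift remains: it equals the share absent times how much higher the absentees were at baseline. For example, 20% × 0.5 SD = 0.10 SD.

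**The case against.** The strongest reply is that little is lost.

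- T1 hypo-intense volume already has paired change and percentage change, and lesion accrual is estimated from new or newly enlarged T2 lesions with a rate and 95% interval. This stands and is the main reason for low priority.
- There is no hypothesis testing (Protocol 12) and no key secondary objective (SAP 2.6). This also stands.
- Fewer than 20% may be absent. The Month 24 MRI window runs from Day 541 to Day 900 (SAP Table 2-3), and the schedule includes MRI at EOT and EOS. Someone who stops after Day 541 with a scan within 30 days of last dose still contributes. This stands, and is why the 10% row is shown.
- A baseline covariate in the single-arm Gd model gives an adjusted mean, not a change, and Gd counts by visit are raw too. This is correct. Even so, T1 hypo-intense number is the only MRI endpoint with none of the three: a change, an incident-lesion definition or a baseline-adjusted model.

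A reader might infer that the plan hides any change in this count, or cannot show accrual at all. The documents do not support that. Baseline MRI characteristics are to be summarised (Protocol 12.2, SAP 2.3.3). The SAP's examples are Gd number and T2 volume, but they are only examples, and the table shells are not in the documents. If a baseline summary of this count is shown, a large shift would be visible. It would still not be a within-participant change.

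A reader might also set the SE of the raw Month 24 mean (about 0.6, 1.2 and 2.3) against 0.12 and claim a 5- to 19-fold gain. That compares a level with a change. The like-for-like comparison is the one in the first table.

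**Conclusion.** The gap is real and modest. A named secondary efficacy endpoint is summarised only as raw counts by visit, while the SAP gives paired change to all three lesion volumes and, in SAP 2.8.3 and 2.8.4.2, to laboratory values and vital signs.

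Under the stated assumptions, pairing is about 2.5 to 9 times more precise than the difference of raw visit means; the gain is smaller if repeat counts agree less closely. A wrong-sign raw difference ranges from uncommon (2% to 23%, absence unrelated to baseline) to frequent (22% to 83%, dependence 0.5 with all 20% absent). No document supports a particular dependence, so the 60% at mean 10 should not be quoted without the 10% beside it.

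The paired change has limits. It does not supply the missing control, and it describes only participants with both scans. If lesion gain itself were related to absence, it would be selective too. Priority is low, because no decision depends on this endpoint.

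**What to change.** In SAP 2.7.1, extend the change-from-baseline definition to the number of T1 hypo-intense lesions, for participants with both a baseline and a post-baseline scan. Use absolute change only, because a baseline count of zero leaves percentage change undefined.

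In SAP 2.7.2, report that paired change at Month 12 and Month 24 by age group, with the n contributing at each visit. Keep the raw count by visit as background. The number and percentage of participants with any increase would be an optional addition.

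The cost is a sentence or two in the SAP and a few table rows. The screening, Month 12 and Month 24 scans are already scheduled (Protocol 8.3.2), so no new data are needed.
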